## **SAMPLE SIZE**

800 participants completing Visit 1: 400 in Chicago and 400 in Houston

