### **Visit 1 Overview**

With identical protocols in Houston and Chicago, persons will receive a short didactic presentation on anal anatomy, practice on pelvic mannequins, and get instructions on doing an ASE or ACE (figure 1). The clinician will then swab the anal canal of each participant, and perform a DARE, without disclosing the results, before leaving participants in private to perform their ASE or ACE. Participants will record their results (as either "normal" or "abnormal") and then get the clinician's DARE result along with any needed referrals; thus, the participant result will be judged against the clinician gold standard. Participants will then complete the post-exam computer-assisted self-interview. At the end of Visit 1, persons will be randomized to a condition of encouraged practice of the ASE (or ACE) or a condition of neither encouragement nor discouragement from practice. Persons will have Visit 2 in 6 months when concordance of self- and companion exam with a clinician DARE will again be assessed. Data collected during these visits will be analyzed to complete the aims.

Figure 1.

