### **Randomization**

At the end of Visit 1, all participants will be randomized to one of two conditions: Arm 1 (practice) or Arm 2 (no practice). One-half of participants in each city will be randomly selected and encouraged to practice the ASE/ACE 3 months before Visit 2. Persons randomized to the control arm will neither be encouraged nor discouraged from practicing the ASE/ACE.

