### **Aim 2**

There is one primary outcome for Aim 2: the association between practice and concordance at Visit 2. Concordance is binary and equals 1 when both participant and clinician identify an abnormality or agree on its absence; thus, the statistical analysis is premised on detecting an anal abnormality, not a cancer. We postulate that practicing the ASE or ACE between visits will be associated with ASE/ACE and DARE concordance at Visit 2. To derive unbiased estimates in multivariable modeling for the association between practice and concordance, we will use directed acyclic graphs to identify potential confounders to include in models (e.g., age, ethnicity, race, city, anxiety, chronic disease, and, for ACE, co-teaching and reported familiarity with a companion’s body) and intermediate variables to exclude from multivariate modeling; however, given successful randomization, bias, including confounding, should be minimized. Both intent-to-treat and per-protocol analyses will be conducted (we expect a similar proportion of persons in the practice and non-practice arms to switch arms of their own accord, i.e., crossover, between visits). The association will be assessed with logistic regression. After univariate analyses, variables where  $p \leq 0.25$ , and which are not intermediate variables, will be added to a multivariable model using backward selection with binary practice (yes/no) retained in the model. After adjustment for potential confounders, factors where  $p < 0.05$  (two-sided) will be considered statistically significant. Adjusted and un-adjusted odds ratios will be reported with 95% confidence intervals. We will use a similar approach to derive unbiased estimates in multivariable modeling for the association between continuous waist size and concordance; however, we will also use ROC curves to ascertain the potential for a threshold effect of waist circumference size on concordance. We will also assess the full set of other study data and their potential associations with concordance. For multiple comparisons we will use the False Discovery Rate. Finally, we will investigate effect modification by age and individual/couple status.

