For the Aim 2 hypothesis, that practice will be associated with concordance in all persons at Visit 2, sample size will be adjusted downward by dropouts and non-resolving abnormalities from Visit 1. We expect 11% of persons ( $n=88$ ) to have an abnormality at Visit 1 (based on pilot data) with most of these being hemorrhoids and condyloma. We conservatively expect 50% of hemorrhoids and condyloma to resolve in 9 months; thus, there will be a minimum of 44 non-resolving events from Visit 1 and another 10% of persons will dropout ( $800-44=756$ ;  $756-76=680$ ). We have 80% power to detect an odds ratio of at least 1.55 or larger if concordance is 85% and  $n=680$ .

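### Aim 2 power is stated as 80% for an odds ratio of 1.55, but 680 participants in two equal arms give about 47% to 59%

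*Combined protocol and SAP*

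**What the plan says.** The sample size paragraph under Statistical Analysis, Aim 2, starts from the whole study (Sample Size section: "800 participants completing Visit 1: 400 in Chicago and 400 in Houston"). It makes two deductions. First, of the 88 people expected to have an abnormality at Visit 1, it says "there will be a minimum of 44 non-resolving events from Visit 1". Second, it says "another 10% of persons will dropout". The remainder is 680, and the paragraph concludes: "We have 80% power to detect an odds ratio of at least 1.55 or larger if concordance is 85" per cent with that n.

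The Randomization section sets equal allocation: "One-half of participants in each city will be randomly selected and encouraged to practice". The Aim 2 analysis text specifies logistic regression of binary concordance on binary practice, with significance at two-sided p<0.05. It also anticipates crossover: "we expect a similar proportion of persons in the practice and non-practice arms to switch arms of their own accord". It gives no crossover rate.

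The deduction for abnormalities rests on this assumption: "We conservatively expect 50% of hemorrhoids and condyloma to resolve in 9 months". The Visit 1 Overview says "Persons will have Visit 2 in 6 months".

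**The concern.** At concordance near 85%, an odds ratio of 1.55 is a difference of only about 5 to 6 percentage points between arms. A sample of 340 per arm looks too small to detect that with 80% power. The paragraph shows how 680 was reached but not how the power was obtained, and it does not say whether 85% is the rate in the control arm, in the practice arm or overall.

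This is the power claim for the single Aim 2 primary outcome and for the only randomised contrast in the study. If true power is near one half, a real effect of the stated size would be missed about as often as found, and a reader relying on the 80% would take a null result as stronger evidence than it is.

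**Working it through.** **Inputs from the plan**

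- Analysed total (Aim 2): 800 − 44 = 756; 10% of 756 ≈ 76; 756 − 76 = 680.
- Allocation (Randomization): one half to each arm, so n = 340 per arm.
- Test (Aim 2): two-sided, alpha 0.05, so z = 1.960.
- Effect (Aim 2): odds ratio 1.55, concordance 85%.

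**Step 1. Turn the odds ratio into two proportions.** With control rate p1, the practice rate is p2 = 1.55·p1 / (1 − p1 + 1.55·p1). The three readings of 85% give:

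- control rate: 0.850 vs 0.898, difference 0.0478
- overall rate: 0.822 vs 0.878, difference 0.0553
- practice rate: 0.785 vs 0.850, difference 0.0648

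**Step 2. Power of the two-proportion test.** With d = p2 − p1 and pbar = (p1 + p2)/2:

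- SE0 = √[2·pbar·(1 − pbar)/n]
- SE1 = √[(p1(1 − p1) + p2(1 − p2))/n]
- Power = Φ[(d − 1.960·SE0)/SE1]

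| 85% is the | d | SE0 | SE1 | (d − 1.960·SE0)/SE1 | Power |
|---|---|---|---|---|---|
| control rate | 0.0478 | 0.02546 | 0.02539 | −0.083 | 0.467 |
| overall rate | 0.0553 | 0.02739 | 0.02730 | 0.061 | 0.524 |
| practice rate | 0.0648 | 0.02962 | 0.02951 | 0.228 | 0.590 |

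The stated 0.80 is not reproduced. A Wald test on the log odds ratio gives 0.463 / 0.520 / 0.586, and simulated likelihood-ratio tests give about 0.47 / 0.52 / 0.60, so the choice of test is not the explanation.

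**Step 3. Try more favourable settings** (control / overall / practice reading):

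- One-sided 0.05, contrary to the plan: 0.592 / 0.647 / 0.707.
- All 800 analysed, two-sided: 0.530 / 0.592 / 0.661.
- All 800 and one-sided: 0.652 / 0.708 / 0.767.
- Splits of 680 from 1:2 to 1:4: less power than 1:1 on each reading.
- 680 in each arm: 0.757 / 0.816 / 0.872.

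Only the last reaches 0.80, on two of its three readings, and the plan's own subtraction shows that 680 is the total. Entering the total as a group size is one possible origin of the figure, but the documents do not show the calculation, so the cause cannot be established.

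**Step 4. What 680 does support, and what OR 1.55 would need**

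| 85% is the | OR detectable at 80% power, 340 per arm | Rates at that OR | n per arm for 80% power at OR 1.55 | Total |
|---|---|---|---|---|
| control rate | 1.99 | 85.0% vs 91.9% | 757 | 1,514 |
| overall rate | 1.84 | 81.2% vs 88.8% | 653 | 1,306 |
| practice rate | 1.74 | 76.5% vs 85.0% | 557 | 1,114 |

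**Step 5. Factors left out of these figures**

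- Crossover. The rate is not given. Assuming that 5% of each arm switches, and that switchers take on the other arm's concordance rate, intent-to-treat power is 0.39 / 0.44 / 0.50; at an assumed 10% it is 0.32 / 0.37 / 0.42.
- Resolution interval. The limiting case, in which none of the 88 abnormalities resolves by 6 months, gives (800 − 88) × 0.9 ≈ 641 analysed and power 0.45 / 0.50 / 0.57.

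**The case against.** The strongest counter-argument is about weight. The central hypothesis concerns sensitivity and specificity in Aim 1. The Aim 2 power figure does not alter the estimand, the test or the randomisation. The plan already promises odds ratios with 95% confidence intervals, which will show the imprecision directly. The change history runs to late 2023 and the timeline ends in 2023, so recruitment may be over and a correction could not change the sample. All of this is fair, and it limits the remedy to the text. It does not make the planning statement true.

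There is one numerical escape. A logistic-regression power formula for a standardised continuous covariate, with n of 680 and an event rate of 85%, gives 0.98 without covariate adjustment and 0.82 with an R-squared of 0.5. The plan states no R-squared, and its exposure is binary and randomised, so that formula does not fit. The precise claim is therefore that no two-arm reading with 680 in total reaches 80%.

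The crossover rates are assumptions and describe an additional loss, so they should not be counted as part of the arithmetic error. The 9-month against 6-month mismatch is a small, separate consistency point: even the extreme case moves power by only about 2 percentage points.

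**Conclusion.** The concern holds: the Aim 2 power statement is wrong as written. For an odds ratio of 1.55, 680 participants in two equal arms give 47%, 52% or 59% power, which is 33, 28 or 21 percentage points below the stated 80%. The chance of missing an effect of that size is therefore 41% to 53%, not 20%.

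This rests only on the plan's own inputs: 680 in total, equal allocation, two-sided 0.05, a binary exposure, and 85% read in each of the three possible ways. It does not depend on settling which reading was intended. The figures assume independent participants and no crossover. Because the statement supports the Aim 2 primary outcome and the only randomised comparison, it must be corrected.

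**What to change.** In the Aim 2 sample size paragraph, state that 680 is about 340 per arm and say which group the 85% describes. Then replace the power claim with the matching pair:

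- control-arm rate: 47% power for OR 1.55; 80% power for OR about 1.99
- overall rate: 52%; OR about 1.84
- practice-arm rate: 59%; OR about 1.74

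Add a sentence that the expected crossover and the correlation within couples are not included in these figures. Restate the resolution assumption for the 6-month interval and carry it into n, which lies between 680 and 641 if 50% to 0% of Visit 1 abnormalities resolve.

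The cost is a wording change, with no extra participants or procedures. The price is a less favourable stated power and a larger detectable odds ratio.

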## BACKGROUND

Anal cancer is a common cancer among gay, bisexual and other men having sex with men (MSM). Its annual incidence is approximately 50-fold and 5-fold higher among HIV-positive MSM and HIV-negative MSM, respectively, compared to the rest of the general population. Like cervical cancer, it is primarily caused by human papillomaviruses (HPV). Unlike cervical cancer, there is no efficacious treatment for anal precancers as there is for cervical precancers. To date, randomized clinical trials have failed to find an efficacious treatment although other trials continue; thus, professional societies recommend an annual Digital Anal Rectal Exam (DARE) for detection of anal abnormalities, including small tumors, among all MSM. But DARE is underutilized, e.g., most persons, regardless of HIV do not receive an annual DARE and most HIV physicians do not perform the exam. Therefore, alternative methods for early detection are needed because early detection of small tumors is associated with >85% 5-year survival.

To increase detection of anal canal tumors, our NCI-funded phase II pilot study in Houston, Texas determined it was feasible to teach MSM to palpate their own, or their companion's, anal canal. Acceptability was 94% among 148 individuals doing the exam on themselves (anal self-exam, ASE) and 92% among 52 couples doing the exam on their companion (anal companion

exam, ACE). There was 93% concordance between the clinician's gold-standard DARE and the participants' ASE or ACE for any anal canal abnormality.

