## BURDEN OF TIME ON PARTICIPANTS DOING THE ASE

Activity	Duration
Pre-Visit 1 - Consenting.	12 min
Pre-Exam Online Survey	8 min
Visit 1	
1. Appointment greeting and photo ID check	1 min
2. Body measurements and COVID-9 symptom check	3 min
3. Anal anatomy and pathology and self-/companion exam education (Visit 1 only)	10 min
4. Anal swab	2 min
5. DARE	2 min
6. Anal-self exam or Anal companion exam	10 min
7. Post-Exam CASI	20 min
8. Results including referral or schedule for treatment if needed	7 min
	Total time
	75 min
Other: for first ~40 persons in each city, second DARE (QA and reliability study)	2 min
Other: estimated 28 persons in each city will have discordant result and clinician will offer to give participant another DARE to adjudicate	2 min
Other: for an estimated 65 persons in each city, a qualitative interview will be done	15 min

Note. Persons in couples doing the ACE at Visit 1 will require about 90 minutes for the visit. For Visit 2, persons will not receive the anal anatomy/pathology and ASE/ACE face-to-face education. Rather, they will be given instructions and asked to do the exam without benefit of a training session with study staff; then the clinician will do a DARE and provide results and any needed referrals during the same face-to face.

Activity	Duration
Immediately before Visit 2	
1. Pre-Visit 2 Pre-Exam Online Survey	10 min
2. Anal-self exam or Anal companion exam	8 min
3. COVID-19 Symptom Online Survey	3 mins
During Visit 2	
4. Appointment greeting, body measurement [weight and waist circumference] ID confirmation	3 min
5. Anal swab, DARE and results with clinician including referral or schedule for treatment if needed	5 min
6. Post-Exam CASI	20 min
	Total clinic time
Other: estimated 25 persons will have discordant result and clinician will offer to give participant another DARE to adjudicate	28 min

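### The Aim 2 claim of 80% power for an odds ratio of 1.55 does not follow from its own inputs: with 680 participants in total and 85% concordance, power is 47% to 59%

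*Combined protocol and SAP*

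**What the plan says.** The Aim 2 part of the Statistical Analysis section names one primary outcome: the association between practice and binary concordance at Visit 2, assessed by logistic regression. The power statement is "We have 80% power to detect an odds ratio of at least 1.55 or larger if concordance is 85" per cent and n is 680.

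The 680 is built up in the same paragraph. It starts from the Sample Size section ("800 participants completing Visit 1: 400 in Chicago and 400 in Houston"), removes 44 people with abnormalities that do not resolve, and then allows that "another 10% of persons will dropout". The Randomization section sets equal allocation: "One-half of participants in each city will be randomly selected and encouraged to practice the ASE/ACE 3 months before Visit 2". The significance rule, in the Aim 2 sentence that opens "After adjustment for potential confounders, factors where", is p below 0.05, two-sided.

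Other places bear on the inputs:

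- Background, on the pilot: "There was 93% concordance between" the clinician's exam and the participants' exams, for anal canal abnormalities.
- The time-burden tables expect 28 discordant results per city at Visit 1. For Visit 2 the entry is "estimated 25 persons will have discordant result", with no denominator.
- On adherence, Aim 2 says "we expect a similar proportion of persons in the practice and non-practice arms to switch arms of their own accord", and plans both intent-to-treat and per-protocol analyses.

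**The concern.** The power sentence supplies almost everything needed to check it: effect size, concordance, sample size, allocation and alpha. Put together, these do not give 80%.

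Two further features make the stated power look optimistic. The assumed 85% is lower than the other concordance figures in the protocol. When the odds ratio is held fixed, moving concordance down from 93% towards 50% increases power, so a low value here is favourable and not cautious. Crossover in both arms is foreseen, yet the sample size is reduced only for dropout and unresolved abnormalities.

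This is the primary outcome of Aim 2 and the only randomised comparison in the study. The stated power tells readers how much weight a non-significant result can bear, so an overstated value misleads them about what the study can rule out.

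**Working it through.** **Inputs.** Analysed total: 800 − 44 = 756; 10% of 756 is 76; 756 − 76 = 680. This arithmetic is correct. Equal allocation gives n = 340 per arm. Alpha is 0.05 two-sided, the odds ratio (OR) is 1.55 and concordance is 85%. The plan does not say which group has 85%, so three readings are tried: control rate, overall rate, practice-arm rate.

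**Formula.** With control rate p0, practice rate p1 and mean p̄:

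p1 = OR·p0 / (1 − p0 + OR·p0)

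power = Φ{ [ |p1 − p0|·√n − 1.96·√(2p̄(1 − p̄)) ] / √(p0(1 − p0) + p1(1 − p1)) }

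**The plan's own case, 85% as the control rate.** p1 = 0.8978 and p̄ = 0.8739. The three terms are 0.0478 × √340 = 0.881; 1.96 × 0.4695 = 0.920; and denominator 0.4683. Power = Φ(−0.083) = 47%. A Wald calculation on the log odds ratio gives 46%, and a simulated likelihood-ratio test from the unadjusted logistic model gives 47%.

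**All readings, no crossover, 340 per arm.** The detectable OR solves the same formula for 80% power. The middle row, 87.8%, is what the hypothesised minimum accuracy implies: 0.11 × 0.70 + 0.89 × 0.90 = 0.878 for the self-exam (0.887 with the companion-exam sensitivity of 78%).

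| Concordance | Taken as | Power for OR 1.55 | Detectable OR at 80% power |
|---|---|---|---|
| 85% | control | 47% | 1.99 |
| 85% | overall | 52% | 1.84 |
| 85% | practice arm | 59% | 1.74 |
| 87.8% | control | 40% | 2.17 |
| 87.8% | overall | 46% | 1.96 |
| 87.8% | practice arm | 52% | 1.81 |
| 93% | control | 26% | 3.00 |
| 93% | overall | 30% | 2.42 |
| 93% | practice arm | 36% | 2.07 |

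At 85%, reaching 80% power for OR 1.55 would take 1,514, 1,306 or 1,114 participants in total on the three readings.

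**Attempts to recover 80%.** A one-sided test at 85% gives 59%, 65% or 71%. Taking 680 as the size of each arm gives 76%, 82% or 87%, so the overall reading lands near 80%, but the plan's subtraction shows 680 to be the total. Reading 1.55 as a risk ratio of discordance (23.25% against 15%) gives 78%, but the text says odds ratio. The sample-size formula for a continuous covariate gives 98%.

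**Where 85% sits.** At Visit 1, 28/400 = 7% discordant, that is 93% concordant. At Visit 2, 25 discordant would be 93.8% concordant if out of 400 and 96.3% if out of 680. At 85%, about 0.15 × 680 = 102 discordant results would be expected.

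**Crossover (rates assumed).** If a fraction c in each arm behaves as the other arm, the intent-to-treat rates become (1 − c)p0 + c·p1 and (1 − c)p1 + c·p0, so the difference shrinks by the factor 1 − 2c. At 85% as the control rate and c = 10%, the rates are 0.8548 and 0.8930 and the odds ratio falls from 1.55 to 1.42. Power at 85% over the three readings is 47%, 52% and 59% with no crossover; 39%, 44% and 50% with 5%; and 32%, 37% and 42% with 10%. This treats 1.55 as the effect under full adherence.

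**The case against.** The best defence concerns the 85%. The endpoint is concordance at Visit 2, when participants examine themselves at home, up to 24 hours before the clinician, six months after training and with no new session. The 93% comes from a pilot and covers anal canal findings only, whereas Aim 1 also counts perianal findings. The 28 per city is a Visit 1 figure and equals the pilot's 7%, so it may not be separate evidence. The Visit 2 figure of 25 has no denominator. A lower expectation for Visit 2 is therefore plausible. This stands: a reader might infer that true concordance will be 93% and that this is why the power fails, but the documents do not establish that, and the shortfall is already present at 85%.

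The same applies to crossover. A reader might infer that ignored crossover breaks the calculation. The plan does foresee it and adds a per-protocol analysis, gives no rate, and does not say whether 1.55 is the intent-to-treat or the full-adherence effect. If it is the intent-to-treat effect, dilution is already inside it and the power for 1.55 does not change.

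It would also go too far to say that only a very large effect is detectable. An odds ratio of 3.0 from a control rate of 93% is 93.0% against 97.6%, or 4.6 percentage points; 1.99 from 85% is 6.9 points (91.9 − 85.0). Nor do the documents show that a null result would be reported as evidence against practice, since 95% confidence intervals are planned.

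None of this rescues the 80%.

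**Conclusion.** The stated power is wrong on the plan's own inputs. At n=680 in total, 1:1 allocation, two-sided 0.05 and 85% concordance, power for an odds ratio of 1.55 is 47% to 59%, and the odds ratio detectable with 80% power is 1.74 to 1.99. This needs no assumption about crossover or a different concordance.

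Two secondary points hold with qualifications. First, 85% is unsourced, lies below the other figures in the protocol (93% in the pilot and at Visit 1, about 88% from the hypothesised minimum accuracy), and errs in the direction that raises power. At 93%, power would be 26% to 36% and the detectable odds ratio 2.1 to 3.0. Secondly, crossover is expected without a rate or an allowance. If 1.55 is the full-adherence effect, an assumed 10% each way lowers intent-to-treat power at 85% to 32% to 42%.

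The calculations are for an unadjusted comparison. They ignore covariate adjustment and any correlation within couples.

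**What to change.** In the Aim 2 power paragraph:

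- Remove the claim of 80% power for an odds ratio of 1.55.
- State whether the concordance is the control, overall or practice-arm rate, where it comes from, and the method of calculation.
- Say whether the target odds ratio is the intent-to-treat or the full-adherence effect.
- Give a short table of the odds ratio detectable with 80% power at n=680, for concordance of 85%, 88% and 93% and for crossover of 0%, 5% and 10% in each arm, with the crossover rates labelled as assumptions.

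In the time-burden table, give the denominator for the 25 discordant results at Visit 2, and either reconcile that figure with the concordance used for power or explain why the two differ.

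The cost is a table in place of one sentence and a less favourable stated power. No participants are added and no procedure changes.
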